BACKGROUND

Exercising is a common strategy used by individuals to get health benefits and to control weight. However, compensatory adaptations in components of energy balance (i.e., energy intake and energy expenditure) are generally observed with exercise (1-3). The degree to which individuals compensate by increasing their food intake and/or decreasing their physical activity level subsequent to the exercise intervention is variable between individuals and may depend on many factors (4, 5). External stimuli such as screen time or music have been reported to increase food intake compared to a control condition with no distraction (6-8). However, previous studies have not looked at the influence of these stimuli on energy balance while exercising, thereby limiting inferences on whether exercising with or without a screen/music leads to different post-exercise energy compensation that may ultimately impact body weight control.

Electronic screen devices and/or music while exercising can serve as motivating factors, making it more pleasant and even easier for some people to exercise (9, 10). This finding may have positive implications for fitness professionals encouraging new exercisers and it is certainly something to keep in mind when one prescribes exercise. However, whether watching a screen or listening to music while exercising impacts components of energy balance is unknown. Gaining information on this issue will help to determine if people should care about the use of personal music players and/or screen devices while exercising with regard to body weight control.

OBJECTIVE AND HYPOTHESIS

The objective of this study will be to examine the effects of watching a screen or listening to music while exercising on acute energy intake and expenditure. We hypothesize that the post-exercise energy compensation will be greater in both conditions with stimuli (i.e., screen and music) compared with the control condition (i.e., exercise alone).

STUDY DESIGN AND RESEARCH METHODS

Study Design

Randomized, 3-condition crossover study (within-subjects experimental design).

Participants

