The primary outcome measure will be post-exercise energy compensation. The food intake outcome will be assessed by using an *ad libitum* test meal immediately after the conditions and a dietary record for the remainder of the day. The energy expenditure outcome will be assessed by using an Actical accelerometer until bedtime. Total energy expenditure (TEE) will be calculated by using the following formula: $TEE = (PAEE \text{ from the Actical} + RMR) \times 1.11$ (28) where the thermic effect of food is fixed at 10% of TEE. The secondary outcome measures will include appetite sensations (VAS) and the RPE (OMNI scale).

Sample Size Calculation

It is estimated that a sample size of 25 participants will provide 90% power at 5% level of significance (two-sided) to detect a minimal group difference of 100 kcal in energy intake and expenditure, assuming a standard deviation of 200 kcal. This is based on previous studies by our group, using a similar crossover design, that compared active video game play with passive video game play in adolescents (29, 30). We used a conservative SD estimate because large variability is generally observed for energy intake (especially with the use of dietary records) and to increase the likelihood of detecting a significant difference between conditions.

Statistical Analysis

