Before statistical analysis, all data will be tested for normality by using the Shapiro-Wilk W test and variance homogeneity and will be log-transformed if necessary. Repeated measures analysis using the mixed model will be used to assess the effect of the 3 interventions on outcome measures, with effects for age, condition, pubertal status and BMI. The models will be adjusted for covariates if they are found to significantly interact with the outcome variables. To account for the fact that repeated measures are taken across conditions, the models will include a participant-specific random effect. Effect sizes will be examined by using the Cohen's *d* method, reflecting the magnitude of the difference between groups in SD units. Cohen's *d* is computed by subtracting the average score of the control group from the average score of the intervention group and then dividing the difference by the pooled SD. Effect sizes are considered negligible if <0.2 , small if between 0.2 and 0.5, moderate if between 0.5 and 0.8, and important if >0.8 . Correlations will be used to examine if the RPE are associated with post-exercise energy compensation. Differences will be considered significant at $P < 0.05$ and data will be presented as mean values and SDs. All statistical analyses will be performed by using SPSS Statistics 23.0 (SPSS Inc, Chicago, IL, USA).

FACILITIES AND EQUIPMENT

The present project will be carried out in our facilities at the Children's Hospital of Eastern Ontario Research Institute in Ottawa. As a national centre of excellence for research, leadership, training and advocacy, our research group strives to provide international leadership and research excellence as it relates to healthy active living and obesity in children and youth (www.haloresearch.ca). All of the proposed methods are routinely performed in our laboratories and the research staff is highly qualified for the

purpose of the study. The personnel needed for this study and the infrastructure and equipment required to conduct the research is available and accessible. The main investigators involved in the proposed research project are also very experienced in designing and conducting studies in this field of research.

KNOWLEDGE TRANSLATION APPROACH

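### The 90% power for 25 participants cannot be reproduced from the stated inputs, because the plan does not say which SD 200 kcal is, gives no within-participant correlation and names no test

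*Combined protocol and SAP*

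**What the plan says.** The Sample Size Calculation section of the combined protocol and SAP says that "a sample size of 25 participants will provide 90% power at 5% level of significance (two-sided"), and continues "to detect a minimal group difference of 100 kcal in energy intake and expenditure, assuming a standard deviation of 200 kcal". For the source of the assumptions it says "This is based on previous studies by our group, using a similar crossover design". It calls the SD conservative on the ground that "large variability is generally observed for energy intake".

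The design is a three-condition crossover in which every participant receives every condition. The Objective and Hypothesis section expects that "the post-exercise energy compensation will be greater in both conditions with stimuli", each compared with exercise alone, so the contrasts of interest are screen against control and music against control. The Statistical Analysis section says "Repeated measures analysis using the mixed model will be used to assess the effect of the 3 interventions on outcome measures", with a participant-specific random effect. It defines Cohen's *d* by "dividing the difference by the pooled SD".

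Neither section gives a within-participant correlation, an SD of the difference or a variance component, and the sample-size paragraph names no test.

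**The concern.** In a within-participant design, the power of a contrast depends on the SD of the within-participant difference. An SD of 200 kcal fixes that quantity only if it is itself the SD of the difference, or if a correlation comes with it. The paragraph supplies neither, so the 90% rests on an input the reader cannot see.

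The power statement is the plan's quantitative case for 25 participants. A planned power of 90% means a 10% chance of missing a true 100 kcal difference on a given contrast; at 67% the chance is about one in three. The plan does not let a reader tell which applies. It also gives one figure for two outcomes that are measured in different ways.

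**Working it through.** **Inputs, all from Sample Size Calculation:** n = 25; difference 100 kcal; SD 200 kcal; "5% level of significance (two-sided"). The correlation ρ is not in the documents, so every value of it below is an assumption.

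**Formulas.** For one contrast, the noncentrality is 100 / SD_diff × √25 = 500 / SD_diff. Power comes from the noncentral t distribution with 24 df (paired t-test) or 48 df (contrast in a three-condition model). If 200 kcal is the SD within a condition, SD_diff = 200 × √(2(1 − ρ)).

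**Trying to reproduce 90%.** The paired t-test reaches 90% at n = 25 only if SD_diff is about 147.9 kcal. The normal approximation gives 500 / (1.960 + 1.282) = 154.2 kcal. Neither value is in the plan.

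**Reading 1: 200 kcal is the SD of the difference.** Noncentrality = 500 / 200 = 2.5.
- Power is 67.0% (24 df), 68.8% (48 df) or 70.5% (normal approximation).
- The standardised difference needed for 90% is 0.6759 (24 df), so 0.6759 × 200 = 135 kcal; with 48 df it is 0.6617 × 200 = 132 kcal.
- For 100 kcal at 90%, the paired t-test would need 44 participants.
- Other tests do not rescue the figure. With equal correlations, the three-condition F test gives 70.7% (means 0/100/100) or 57.4% (0/50/100). The two stimulus conditions averaged against control give 80.7% (48 df).

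**Reading 2: 200 kcal is the SD within a condition.** Paired t-test, 24 df:

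| Assumed ρ | SD_diff (kcal) | Noncentrality | Power |
|---|---|---|---|
| 0 | 282.8 | 1.77 | 39.6% |
| 0.3 | 236.6 | 2.11 | 52.7% |
| 0.5 | 200.0 | 2.50 | 67.0% |
| 0.7 | 154.9 | 3.23 | 87.2% |
| 0.8 | 126.5 | 3.95 | 96.6% |

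Solving for 90%: ρ = 1 − SD_diff² / (2 × 200²) = 1 − 147.95² / 80,000 = 0.73 with 24 df. With 48 df the required SD_diff is 151.1 kcal and ρ = 0.71. The F test needs 0.69 to 0.77, depending on the pattern of means.

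**Reading 3: 200 kcal is the residual SD of the mixed model.** SD_diff = 200 × √2 = 282.8 kcal, and power is 39.6% (24 df) or 41.0% (48 df).

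**Which reading the text favours.** The sample-size paragraph speaks of a difference between groups and of the spread of energy intake, and the effect-size definition uses a pooled SD. These point to reading 2 but do not settle it.

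**Two outcomes, one figure.** Under Outcome Measures, total energy expenditure is 1.11 × (PAEE + RMR), and RMR is measured once, at the preliminary visit. If expenditure means this total, the same RMR enters all three conditions and cancels from within-participant differences. Intake, from a test lunch plus a dietary record, has no such fixed component. There is no reason to expect one correlation to serve both.

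**The case against.** The strongest reply is that this is an omission, not an arithmetic error. On the reading the wording favours, 25 participants, 100 kcal, 200 kcal and 90% fit together at a correlation of about 0.7. That value could have come from the group's earlier crossover trials, which the paragraph cites as its basis. The documents also give some qualitative support for a high correlation: the food menu is described as reliable in adolescents, breakfast is identical at each visit, and RMR is common to all conditions.

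Much of this stands. The 90% is not shown to be impossible, and it cannot be said that no correlation was used, only that none is shown. But a cited source is not a stated value, and none of the qualitative points establishes 0.7. The same paragraph warns of large variability, especially with dietary records. Calling the SD conservative does not help either, because a cautious SD within a condition says nothing about the correlation.

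It is also fair that power is a planning quantity. It changes no estimate, interval or test, and a non-significant contrast is better read from its confidence interval.

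A reader might go further and infer that the trial has only 67% power, or that it needs 44 participants. The documents do not support that: both figures require 200 kcal to be the SD of the difference (or, equivalently, a correlation of 0.5), which the plan does not say. A reader might also notice that 25 is what a one-sided 5%, 80%-power normal approximation gives with an SD of the difference of 200 kcal. That is a coincidence of figures and not evidence of how the number was chosen; the plan states two-sided and 90%.

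**Conclusion.** The point holds as a reporting defect: the stated inputs do not deliver the stated power without an input the plan omits. Depending on what 200 kcal means, per-contrast power for 100 kcal is about 67% (SD of the difference), about 40% (residual SD), or anywhere from about 40% to 97% for assumed correlations of 0 to 0.8 (SD within a condition), with 90% reached at about 0.7. There is no basis in the documents for treating 67% as a floor.

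These figures assume 25 complete participants, equal variances and correlations across conditions, and no multiplicity adjustment; none is planned. The choice between 24 and 48 df moves power by about 2 percentage points or less in the cases compared and does not affect the conclusion. The plan should be corrected, but the defect does not invalidate the design or the analysis.

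**What to change.** Keep 25 participants. State which SD 200 kcal is, name the test or contrast, say that power is per contrast, and restate it as follows.

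- **If it is the SD of the difference:** *Taking 200 kcal as the SD of the within-participant difference, 25 participants give about 67% power for 100 kcal per contrast, or 90% power for about 135 kcal (paired t-test, two-sided 5%).*
- **If it is the SD within a condition:** *Taking 200 kcal as the SD within a condition, and correlations of [value] for intake and [value] for expenditure from our earlier crossover trials, 25 participants give [power] and [power] for 100 kcal per contrast ([named test], two-sided 5%).* Keep 90% only for an outcome whose correlation reaches about 0.7.
- **If it is the residual SD:** say so and state about 40% per contrast.
- **If no correlation can be sourced for the within-condition reading:** withdraw the 90% and give power only as a grid over assumed correlations, labelled illustrative and including values below 0.5.

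The cost is a few sentences and looking up two correlations in the group's own earlier data. No participants are added and the analysis is unchanged. The downside is that the stated power may become less favourable, and intake and expenditure may need separate figures.

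### The single 90% power figure is at best for one stimulus-versus-control contrast under an unstated correlation, and is not shown to be the power to find both screen and music above control

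*Combined protocol and SAP*

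**What the plan says.** The design is a "Randomized, 3-condition crossover study (within-subjects experimental design"), so every participant supplies all three conditions. The Objective and Hypothesis section states: "We hypothesize that the post-exercise energy compensation will be greater in both conditions with stimuli (i.e., screen and music) compared with the control condition".

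The Sample Size Calculation gives one power statement. With 25 participants and a two-sided test at 5%, it puts power at 90% for the following target: "to detect a minimal group difference of 100 kcal in energy intake and expenditure, assuming a standard deviation of 200 kcal". It cites two earlier crossover studies by the same group and calls the SD conservative. It gives no within-participant correlation, no type of SD and no named pair of conditions.

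The Statistical Analysis section plans a mixed model with a participant random effect for the three conditions. Its only decision rule is "Differences will be considered significant at $P < 0.05". It names no contrasts and does not say what pattern of results would confirm the hypothesis.

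**The concern.** A power figure for one pairwise difference is not the power for a hypothesis about two. If screen and music must both be shown to exceed control, the probability of success is lower than for either alone. This costs power; it does not inflate the false-positive rate. The documents do not tie the 90% to either quantity, and it cannot be reproduced without an assumption they leave out.

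What is at stake is how a mixed result is read. If both true effects are 100 kcal, a trial in which only one contrast reaches significance is a fairly common chance outcome. A reader who takes 90% as the power for the whole hypothesis will not expect it, and may take it as evidence that the two stimuli differ.

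**Working it through.** **Inputs from the documents.** n = 25, difference 100 kcal, SD 200 kcal, two-sided 5%, three conditions within participant. **Not given, so assumed:** the SD type and the within-participant correlation ρ. Equal variances and equal correlations across conditions are also assumed.

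**Step 1. Can the 90% be reproduced for one contrast?** For a paired comparison the noncentrality is 100 × √25 / SDdiff = 500 / SDdiff, tested with 24 df.

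- SDdiff = 200: noncentrality 2.5. Normal approximation Φ(2.5 − 1.96) = 70.5%; exact noncentral t, 67.0%. The mixed model's pooled error (48 df) gives 68.8%.
- 200 kcal per condition: SDdiff = 200 × √(2(1 − ρ)).

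| ρ | SDdiff (kcal) | Power, one contrast (paired t) |
|---|---|---|
| 0 | 282.8 | 39.6% |
| 0.5 | 200.0 | 67.0% |
| 0.6 | 178.9 | 76.5% |
| 0.7 | 154.9 | 87.2% |
| 0.75 | 141.4 | 92.4% |
| 0.8 | 126.5 | 96.6% |

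Solving for exactly 90% with the t test gives SDdiff = 147.9 kcal, so ρ = 1 − 147.9² / (2 × 200²) = 0.73. The normal approximation gives SDdiff = 154.2 and ρ = 0.70. The printed 90% therefore needs a per-condition SD and a correlation of roughly 0.70 to 0.73, neither of which is stated.

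**Step 2. Power for both contrasts.** The two contrasts share the control day. Each difference has variance 2σ²(1 − ρ) and their covariance is σ²(1 − ρ), so they correlate 0.5. If each has 90% power, z = 1.2816, and the bivariate normal probability that both succeed is Φ₂(1.2816, 1.2816; 0.5) = 83.2%. Varying the correlation between contrasts gives 81.0% at 0 and 85.1% at 0.75.

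**Step 3. Simulation check.** Three-condition crossovers (400,000 runs), n = 25, both true effects 100 kcal:

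| SDdiff | Test | One contrast | Both | Exactly one |
|---|---|---|---|---|
| 148 | paired t | 90.0% | 83.2% | 14% |
| 148 | mixed model, pooled error | 91.2% | 85.3% | 12% |
| 200 | paired t | 66.9% | 51.6% | 31% |
| 200 | mixed model, pooled error | 68.8% | 54.5% | 29% |

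The mixed model's 85% arises because, at the same SD, each contrast has slightly more than 90% power.

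**Step 4. What would give 90% for both?** Each contrast would need about 94.3% power. In the Step 1 table that corresponds to a correlation between 0.75 and 0.80.

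**The case against.** The strongest reply is that the plan writes no rule that both contrasts must be significant. The Sample Size Calculation attaches its power to detecting a difference, not to confirming the hypothesis, and quoting power per comparison is ordinary practice. The hypothesis can be read as two directional expectations, each reported on its own. This stands: the joint requirement is inferred from the wording of the hypothesis, so a reader should not conclude that the plan claims 90% for the joint result or sets a formal success rule and then misses it. What remains is that the only power figure is tied neither to a named contrast nor to the hypothesis.

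A second reply is that the earlier crossover studies may supply a high correlation, and that with ρ between 0.75 and 0.80 joint power would itself reach 90%. That is possible, but the document prints no correlation and does not say that the figure is joint.

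A reader might also go too far in two directions:

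- One is to accept that 90% is sound for each single contrast. The printed inputs alone do not show it; they give about 67% if 200 kcal is the SD of the difference.
- The other is to take the mention of intake and expenditure as requiring significance on both, which would push power lower still. The plan names one primary outcome, post-exercise energy compensation. It describes compensation as acting through intake, activity or both, and gives no correlation between the two. No figure for both outcomes is supportable.

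**Conclusion.** The point holds in a limited form. The 90% is at best the power for one stimulus-versus-control contrast, and only with 200 kcal as the per-condition SD and a within-participant correlation near 0.73. Granting that, power to show both contrasts is about 83% (paired t) to 85% (mixed model), a shortfall of 5 to 7 points against the printed figure. If 200 kcal is the SD of the difference, it is about 67–69% for one contrast and 52–55% for both.

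These figures assume true effects of exactly 100 kcal in both conditions, equal variances and correlations, and complete data on all 25 participants. The joint figure falls below the per-contrast figure under either SD reading. The fault is an incompletely specified power statement; the documents do not show that the trial fails a rule it set for itself.

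**What to change.** In the Sample Size Calculation:

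- Name the two contrasts: screen versus control and music versus control.
- State whether 200 kcal is the per-condition SD or the SD of the within-participant difference, and give the within-participant correlation with its source.
- Replace the unqualified 90% with two figures that follow from those inputs: power per contrast and power for both. Do not print 90% per contrast without the correlation that supports it.
- Say whether the hypothesis is confirmed only if both contrasts are significant, or whether the two are reported as separate hypotheses. In the latter case the per-contrast figure is the relevant one.
- Give no power for intake and expenditure together unless the plan states that both must be significant.

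The cost is a few sentences and a less favourable stated power. No change in enrolment is proposed. For scale only: if 25 truly gave 90% per contrast, 90% for both would correspond to about 30 participants (25 × 1.19), and if 200 kcal is the SD of the difference, 90% for a single contrast would correspond to 44 by the t test.
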